6.3 SUBJECT SETS ANALYSED

The following subject sets are planned to be investigated:

Table 6.3: 1 Definition of populations

Analysis Population	Definition
Screened subjects set (SCR)	All subjects enrolled in the study, following the receipt of informed consent.
Observed subjects set (OBS)	All subjects, from the SCR, who are eligible to enter the observation period.
Per-protocol set (biomarker subjects) (PPSBM)	All subjects, from the OBS, who have no IPDs affecting the clinical or biomarker assessments.
MRI set	All subjects, from the PPSBM, with MRI performed at baseline

Table 6.3:2 shows which analysis set is used for each class of assessment:

[figure not shown]
Table 6.3: 2 Subject sets for planned analyses

Planned analysis	Subject set
Disposition	Screened subjects set
Demographic data	Observed subjects set
	Per-protocol set (biomarker subjects)
Clinical and biomarker assessments	Per-protocol set (biomarker subjects)
Safety analyses	Observed subjects set

[figure not shown]
All analyses will be performed on observed cases (OC). Note that the number of subjects with available data for an assessment may differ. For details, see Section 6.6 "Handling of missing data".

TSAP for BI Study No: 352.2069 Proprietary confidential information © 2022 Boehringer Ingelheim International GmbH or one or more of its affiliated companies

TSAP for BI Study No: 352.2069 Proprietary confidential information © 2022 Boehringer Ingelheim International GmbH or one or more of its affiliated companies

6.5 POOLING OF CENTRES

No pooling of centres will be performed.

6.6 HANDLING OF MISSING DATA AND OUTLIERS

Every effort should be made to collect complete data for each time point at each test day.

6.6.1 Observed case (OC) analysis

Observed case analysis implies the analysis of data exactly as observed, without the use of any imputation techniques.

6.6.2 Missing or partial dates

For incomplete date information, e.g. date stopping smoking or exacerbation dates, the midpoint of the possible interval will be used. If only the year is present, the day and month

will be imputed as 01 July; if year and month are present, the day will be imputed as 15. If the year is missing, the date will be considered missing.

For partial start and stop dates for background medication, concomitant therapies, and additional treatments, the following derivations will be used to impute the missing dates where deemed necessary:

- If the day of the end date is missing, then the end date is set to last day of the month.
- If the day and month of the end date are missing, then the end date is set to 31st December of the year.
- If the day of the start date is missing, then start date is set to first day of the month.
- If the day and month of the start date are missing, then the start date is set to 1st January of the year.

All other cases need to be assessed by the study team on an individual basis, using the above points as guidance.

6.6.3 Spirometry and Body plethysmography

No imputation method will be implemented for missing data.

In case of use of restricted medication during the observational period (biologic antagonists or other investigational drugs), all respective data (see Section 5.3.1.1 and Section 5.3.1.2) collected from the first use of these medications onwards will be excluded from all analyses. Regarding concomitant medication and the restrictions stated in CSP Section 4.2.2.1, only respective data during the 15 day window will be excluded from analysis. These exclusions are documented in the conmed log file [c28419093].

If an exacerbation (or MESIs like pneumonia, pulmonary fibrosis, asthma-chronic pulmonary disease overlap syndrome) occurred or is not resolved 15 days prior to a visit with PFT testing, respective data from this visit will be excluded from the analysis. If a MESI is considered relevant to impact data from all follow up visits, all collected data from the MESI onset date onwards will be excluded from the analysis. These exclusions are documented in the MESI log file [c28782045].

Findings identified during the imaging MQRM process were considered for data censoring. These exclusions are documented in the censoring log file [c32908066].

For subjects who re-started smoking during the observational period, all data collected from that timepoint onwards will be excluded from all analyses. These exclusions are documented in the iPD log file [c26595312].

Regarding timing of spirometry, all data collected at post-baseline visits which are not within 3 hours from the timing of Visit 2 and are outside the 6.00 a.m. and 12.00 a.m. interval will be excluded from analyses.

6.6.4 Diffusing capacity of the lungs for carbon monoxide

In case of use of restricted medication during the observational period (biologic antagonists or other investigational drugs), all DLCO data (see Section 5.3.1.3) collected from the first use of these medications onwards will be excluded from all analyses. Regarding concomitant medication and the restrictions stated in CSP Section 4.2.2.1, only respective data during the 15 day window will be excluded from analysis. These exclusions are documented in the conmed log file [c28419093].

If an exacerbation (or MESIs like pneumonia, pulmonary fibrosis, asthma-chronic pulmonary disease overlap syndrome) occurred or is not resolved 15 days prior to a visit with PFT testing, DLCO data from this visit will be excluded from the analysis. If a MESI is considered relevant to impact data from all follow up visits, all collected data from the MESI onset date onwards will be excluded from the analysis. These exclusions are documented in the MESI log file [c28782045].

Findings identified during the imaging MQRM process were considered for data censoring. These exclusions are documented in the censoring log file [c32908066].

For subjects who re-started smoking during the observational period, DLCO data collected from that timepoint onwards will be excluded from all analyses. These exclusions are documented in the iPD log file [c26595312].

Since most intra-session variability is technical, rather than physiological, the mean of acceptable DLCO measurements is reasonable to be reported. Moreover, there should be at least two acceptable measurements that meet the repeatability requirement of either being within 1 mmol/min/kPa of each other, or within 10% of the overall highest value. Therefore, in order to preserve data quality, all subjects with only one DLCO measurement should be set to missing. Following the rationale of MacIntyre et al (2005) [6], imputation rules, given below, will be implemented to ensure that all acceptable DLCO measurements adhere to the repeatability requirement criteria:

Assume $x1 \le x2 \le x3$ denote the single DLCO measurements. Then let

- c0 = x3 * 10%
- c12 = x2 x1
- c23 = x3 x2
- c13 = x3 x1
- x = DLCO value to be used.

[figure not shown]
If $(c13 \le c0)$ or $(c13 \le 1 \text{ mmol/min/kPa})$, then x = (x1 + x2 + x3) / 3.

Else, if $(c23 \le 1 \text{ mmol/min/kPa})$ or $(c23 \le c0)$, then x = (x2 + x3) / 2.

Else, if $(c12 \le 1 \text{ mmol/min/kPa})$, then x = (x1 + x2) / 2.

Else, x = missing.

If a DLCO measurement is excluded for the calculation of mean DLCO based on the above rules, the respective VA value will also be excluded from the calculation of the mean VA.

6.6.7 Safety

With regard to the safety analysis, no imputation of safety data is foreseen (observed case analysis) except for missing or incomplete AE dates. Missing or incomplete AE dates are imputed according to BI standards [7].

6.6.8 Symptom questionnaires

mMRC

• No imputation will be implemented for missing data.

CAT

- If responses to no more than two questions are missing, then missing scores for individual questions will be replaced by the mean score of the non-missing questions [8].
- If more than two questions are missing then the total score will not be calculated.

SGRQ

- Missing questionnaire responses will be handled according to the guidelines outlined in the SGRQ Manual [9]. Missing responses within patients' questionnaires will not be imputed, and will remain as is, with one exception:
 - Question 5 asks "how many severe or very unpleasant attacks of chest trouble" patients have had during the past 4 weeks, whilst Question 6 asks "how long did the worst attack of chest trouble last?"
 - It is possible that patients may answer Question 5 as 'No attacks' and then go
 on to state a length of time for the worst attack in Question 6. In this case, the
 response to Question 6 will be set to missing to be consistent with Question 5.
 - As stated below, the SGRQ guidelines for calculation of the Symptoms component allow for a maximum number of missing responses. However, due to the relationship between Questions 5 and 6, the response to Question 6 should be missing if Question 5 is answered as 'No attacks'. Therefore, a missing response to Question 6 will not be included in the count of missing responses for the Symptoms component in the following cases:
 - Questionnaires where the patient has deliberately not answered Question 6, due to answering Question 5 as 'No attacks', or
 - Question 6 has been set to missing
- If there are more than 2, 4, or 6 missed items in the Symptoms, Activity, or Impacts component, respectively, then the component score will be set to missing. A total score will not be calculated, unless a score exists for all three components (Symptoms, Activity, and Impacts).

For patients who re-started smoking during the observational period, all data collected from that timepoint onwards will be excluded from all analyses.

6.7 BASELINE, TIME WINDOWS AND CALCULATED VISITS

Definition of baseline

Analysis windows for all assessments during the study are given in the following tables. The date of the initial visit 2 will be used as study day 1 for the time windowing (including subjects with a repeated visit 2). If more than one value is available within one time window the one which is closest to the planned time/day is used for analysis. In case two values are equidistant from the planned time/day, then the last one will be picked.

Table 6.7: 1 Time windows for lung function assessment – Spirometry, pulse oximetry, lung diffusion capacity

Interval	Label	Visit	planned day	Window [days]	Analysis Window [days]
Observational period	Baseline	2	1	1	≤ 28
Observational period	Week 12	3	84	77 to \leq 91	29 to ≤ 130
Observational period	Week 26	4	182	$168 \text{ to} \leq 196$	131 to \leq 273
Observational period	Week 52	5	364	$350 \text{ to} \leq 378$	$274 \text{ to } \leq 546$
Observational period	Week 104	6	728	714 to \leq 742	$547 \text{ to } \leq 910$
Observational period	Week 156	7	1092	$1078 \text{ to} \leq 1106$	≥ 911

Table 6.7: 2 Time windows for lung function assessment - Body plethysmography

Interval	Label	Visit	planned	Window [days]	Analysis
			day		Window [days]
Observational period	Baseline	2	1	1	≤ 28
Observational period	Week 12	3	84	77 to \leq 91	29 to ≤ 130
Observational period	Week 26	4	182	$168 \text{ to } \leq 196$	131 to \leq 273
Observational period	Week 52	5	364	$350 \text{ to } \leq 378$	$274 \text{ to } \leq 546$
Observational period	Week 104	6	728	714 to \leq 742	$547 \text{ to } \leq 910$
Observational period	Week 156	7	1092	$1078 \text{ to} \le 1106$	≥ 911

Table 6.7: 3 Time windows for lung function assessment – BODE index

Interval	Label	Visit	planned day	Window [days]	Analysis Window
			•		[days]
Observational period	Baseline	2	1	1	≤ 28
Observational period	Week 104	6	728	714 to \leq 742	29 to \leq 910
Observational period	Week 156	7	1092	$1078 \text{ to} \leq$	≥ 911
_				1106	

Table 6.7: 4 Time windows for lung function assessment – 6-minute walk test

Interval	Label	Visit	planned day	Window [days]	Analysis Window [days]
Observational period	Baseline	2	1	1	≤ 28
Observational period	Week 104	6	728	$714 \text{ to } \le 742$	29 to \leq 910
Observational period	Week 156	7	1092	$1078 \text{ to} \le 1106$	≥ 911

Table 6.7: 5 Time windows for soluble biomarker assessment – blood and induced sputum

Interval	Label	Visit	planned	Window	Analysis
			day [days]		Window
					[days]
Observational period	Baseline	2	1	1	≤ 28
Observational period	Week 12	3	84	77 to \leq 91	29 to ≤ 130
Observational period	Week 26	4	182	$168 \text{ to} \leq 196$	131 to \leq 273
Observational period	Week 52	5	364	$350 \text{ to} \leq 378$	274 to \leq 546
Observational period	Week 104	6	728	714 to \leq 742	$547 \text{ to } \leq 910$
Observational period	Week 156	7	1092	1078 to \leq	≥ 911
				1106	

Table 6.7: 6 Time windows for imaging biomarker assessment – CT

Interval	Label	Visit	planned day	Window [days]	Analysis Window
			·		[days]
Observational period	Baseline	2	1	1	≤ 28
Observational period	Week 52	5	364	$350 \text{ to} \leq 378$	29 to \leq 546
Observational period	Week 104	6	728	714 to \leq 742	$547 \text{ to } \leq 910$
Observational period	Week 156	7	1092	1078 to \leq	≥ 911
				1106	

Table 6.7: 7 Time windows for imaging biomarker assessment – MRI

Interval	Label	Visit	planned	Window [days]	Analysis
			day		Window
					[days]
Observational period	Baseline	2	1	1	≤ 28
Observational period	Week 26	4	182	$168 \text{ to } \leq 196$	29 to \leq 273
Observational period	Week 52	5	364	$350 \text{ to } \leq 378$	$274 \text{ to } \leq 546$
Observational period	Week 104	6	728	714 to \leq 742	$547 \text{ to } \leq 910$
Observational period	Week 156	7	1092	$1078 \text{ to } \leq 1106$	≥ 911

Table 6.7: 8 Time windows for symptom questionnaire – mMRC, CAT, SGRQ-COPD

Interval	Label	Visit	planned	Window	Analysis
			day	[days]	Window
					[days]
Observational period	Baseline	2^{1}	1	1	≤ 28
Observational period	Week 52	5	364	$350 \text{ to} \leq 378$	29 to \leq 546
Observational period	Week 104	6	728	714 to \leq 742	$547 \text{ to } \leq 910$
Observational period	Week 156	7 1092 1		1078 to \leq	≥ 911
				1106	

¹ Visit 1 for mMRC (Screening)

Table 6.7: 9 Time windows for safety assessment – physical examination, vital signs

Interval	Label	Visit	planned day	Window [days]	Analysis Window
Screening	Baseline	1	-28 to -	1	[days] < 28
Sercening	Dascinic	1	1	1	
Observational period	Week 52	5	364	$350 \text{ to} \leq 378$	29 to \leq 546
Observational period	Week 104	6	728	714 to \leq 742	$547 \text{ to } \leq 910$
Observational period	Week 156	7	1092	$1078 \text{ to } \leq 1106$	≥ 911

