5.8.1.2 Collection of sputum (in a subset of subjects only)

Induction and collection of sputum will be done in all subjects at selected sites only and samples will be taken at time points indicated in the [flowchart](#).

In addition, subjects who have signed informed consent might be asked to provide an induced test sputum sample at the screening visit in order to assess the sputum processing capabilities at the investigational site. In this case the test sputum induction should take place at least 20 days prior to the first subject performing Visit 2 at the site.

The provided sputum samples will be obtained and processed according to the manual for sputum induction and processing provided in the ISF. The processing of sputum samples should start immediately, but no later than 1 hour after the sample has been taken.

Sputum induction will be started following all other visit assessments and should be done with the subjects being in a state of bronchodilation.

Patients are allowed to take their usual COPD medication before sputum induction. In addition, pre-treatment with salbutamol (albuterol) should be repeated if time between morning administration of salbutamol (albuterol) for post-bronchodilator PFT measurement and start of sputum induction is exceeding 4 hours.

Subjects who are not able to produce an acceptable sputum sample at Visit 2 and Visit 2 Retest as determined by the central overread will continue in the study, however, no sputum induction should be performed for the remainder of the study (from Visit 3 to Visit 7/discontinuation).

Detailed instructions for sputum induction and processing, storage and shipment are provided in the site's ISF.

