6.1.1.2 Sputum induction (at selected sites only)

Sputum induction at Visit 2 can be rescheduled up to 3 days. If the subject is unable to produce an adequate sample of the sputum or a sputum sample of acceptable quality at visit 2 (after feedback from the vendor), repeat sputum induction should be performed. An interval of at least 3 full days and up to 21 days should be observed between repeat sputum induction procedures. All other Visit 2 procedures should have been completed on the originally scheduled Visit 2 date.

If sputum induction procedure at Visit 2 needs to be repeated, subject will complete only the sputum induction procedure at the repeat visit. In this case, sputum induction should be started within 15 min to 4 hours after salbutamol (albuterol) inhalation. Salbutamol (albuterol) can be self-administered by the subject under the supervision of the staff performing the sputum induction according to the inhalation procedure described for the post-bronchodilator testing (four separate doses at approximately 30 sec interval, see [Section 5.4](#)).

Sputum induction procedures at Visits 3 - 7 will not be repeated if the subject is unable to produce sputum or if the sputum sample quality is not acceptable. If the sputum induction and processing procedure cannot be scheduled during the regular study Visits 3 to 7, it should be rescheduled within 21 days after the visit. In this case, administration of salbutamol (albuterol) should be performed prior to the procedure.

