7.3.1.3 ANOVA Models and Logistic regression for Baseline Biomarker Values

Baseline values are defined as the last measurement taken by the end of Visit 2.

To compare baseline biomarkers and clinical assessments across subject groups, analysis of covariance (ANOVA) models for continuous variables and logistic regressions for ordinal and categorical variables will be conducted. Demographic variables and baseline disease status are adjusted to account for potential imbalance in baseline values. A detailed list of covariates will be discussed in TSAP.

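### As printed, the SAP 6.7 window rule takes the first Visit 2 sputum value over the Visit 2 Retest whenever both values are retained, although the retest is done only because the first sample failed

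*SAP*

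**What the plan says.** **SAP 6.7** has three rules that act together.

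- Anchor: "The date of the initial visit 2 will be used as study day 1 for the time windowing (including subjects with a repeated visit 2").
- Selection: "If more than one value is available within one time window the one which is closest to the planned time/day is used for analysis".
- Ties: "In case two values are equidistant from the planned time/day, then the last one will be picked".

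Table 6.7: 5, for blood and induced sputum, gives the baseline visit planned day 1 and an analysis window of day 28 or earlier. The visible rule sets no condition on sample quality.

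**Protocol 6.1.1.2** lets the Visit 2 induction move by up to 3 days. It calls for a repeat in this case: "If the subject is unable to produce an adequate sample of the sputum or a sputum sample of acceptable quality at visit 2". On timing it says: "An interval of at least 3 full days and up to 21 days should be observed between repeat sputum induction procedures". Only the sputum procedure is done at the repeat visit.

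**Protocol 5.8.1.2** stops further sputum induction, while keeping the subject in the study, for this group: "Subjects who are not able to produce an acceptable sputum sample at Visit 2 and Visit 2 Retest as determined by the central overread". A subject who passes at the retest therefore goes on giving sputum through Visit 7.

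**Protocol 7.3.1.3** has its own definition: "Baseline values are defined as the last measurement taken by the end of Visit 2".

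**SAP 5** defines absolute and relative change from baseline for continuous assessments generally.

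**The concern.** A closest-to-target rule is a sensible default when duplicate values are of equal standing. Here they are not. The second baseline induction exists because the first was judged unfit, so the order of the two samples carries information about their quality. A rule based on distance from day 1 prefers the earlier sample and ignores that information.

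The SAP's reference to a repeated Visit 2 suggests that this situation was in view. In the visible protocol, sputum is the only Visit 2 procedure with a described repeat. Fixing day 1 at the initial visit is reasonable for timing the follow-up windows, but combined with the distance rule it decides the baseline against the retest.

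If a result from the rejected sample is stored, it becomes the subject's baseline sputum value. It is subtracted in every later absolute change, and it enters both numerator and denominator of every relative change. It would also enter the baseline summaries of soluble biomarkers.

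**Working it through.** The documents give no figure on this point to reproduce. The check applies the printed rule to the day pairs that the protocol allows.

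**Inputs**

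- Planned day 1, window up to day 28: SAP Table 6.7: 5.
- Day 1 is the initial Visit 2; take the smallest distance to the planned day; take the last value if tied: SAP 6.7.
- First induction on day d1 = 1 to 4, that is, day 1 or up to 3 days later: Protocol 6.1.1.2. I read the shift as a delay, because sputum is to be collected after all other visit assessments.
- Gap g from first to repeat induction of 3 to 21 days: Protocol 6.1.1.2. I ran g to 22 to allow for a lenient count of full days.

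**Step 1: is the retest inside the baseline window?** The retest day is d2 = d1 + g.

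- Earliest: 1 + 3 = day 4.
- Latest: 4 + 21 = day 25, or 4 + 22 = day 26 on the lenient count.

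Both limits are below 28, so the retest always competes for baseline.

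**Step 2: which value is closer to day 1?**

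- First sample: d1 − 1, which is 0 to 3 days.
- Retest: d2 − 1 = (d1 − 1) + g.
- Difference: g, which is at least 3 days.

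The first sample is always closer. There are 4 values of d1 and 20 values of g (3 to 22), so 4 × 20 = 80 pairs. The first sample is selected in 80 of 80.

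**Step 3: can the tie rule help?** A tie needs g = 0, which cannot occur. The last-value provision never reaches the retest.

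**Step 4: what if only one value exists?** If the first induction left no value, the retest is the only candidate in the window and is selected on every possible day.

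| Values held in the baseline window | Value selected by SAP 6.7 |
|---|---|
| First sample and retest | First sample, 80 of 80 pairs |
| Retest only | Retest, always |

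**Step 5: how many subjects?** The affected share of sputum-site subjects is p × r, where p is the share retested and r is the share of those whose rejected first sample has a retained result. Neither is in the documents. With r between 0 and 1, the share lies between zero and p.

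**Step 6: the two baseline definitions.** Under Protocol 7.3.1.3 the retest is baseline if it counts as part of Visit 2, and the first sample is baseline if it does not. The name Visit 2 Retest suggests the former. The separate repeat visit in 6.1.1.2, after all other Visit 2 procedures are complete, leaves room for the latter.

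**The case against.** The strongest objection is that the rule acts only on available values, and nothing visible shows that a rejected sample leaves one. One of the two triggers for the repeat is failure to produce an adequate sample, where there is normally nothing to assay. For the other, unacceptable quality, the documents do not say whether the sample is assayed or its result kept. A reader might infer that every retested subject gets a failed sample as baseline; the documents do not support that. This part of the objection stands and makes the point conditional.

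The public text is also incomplete where a quality rule could sit. SAP 6.6.5 and 6.6.6 are not shown, nor is any text directly under the heading on the definition of baseline in 6.7. A reader might infer that the SAP has no quality rule for sputum. That cannot be concluded. What can be said is that the printed selection rule, read alone, gives the wrong order when two values are present.

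A reader might also infer that the SAP plainly contradicts the protocol's baseline definition. That holds only if the retest counts as Visit 2, which the protocol leaves open. The two texts need reconciling, but they are not in proven conflict.

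Finally, all tests in the study are exploratory (Protocol 7.2), sputum is collected at selected sites only, and none of the main outcomes in SAP 5.1 (adjusted lung density, FEV1, exacerbations) uses sputum. All of this stands and lowers the severity. It does not remove the point, because the direction of the printed rule follows from its own wording.

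**Conclusion.** The point holds in conditional form. Whenever the first Visit 2 sputum sample and the Visit 2 Retest both have a retained value, SAP 6.7 as printed selects the first, which is the one the retest was meant to replace. This is certain given the printed rule and the protocol's timing, with any shift of the first induction read as a delay.

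Whether it affects any subject depends on two things the documents do not show: whether rejected samples produce stored results, and whether a section not shown already excludes them. If they produce none, or are already excluded, nothing changes. The number affected cannot be estimated from the documents and may be zero. The consequence is limited to baseline values and changes from baseline of exploratory sputum biomarkers at selected sites. Severity is low.

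**What to change.** Add to SAP 6.7, for baseline induced sputum only:

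- Candidates are Visit 2 or Visit 2 Retest samples accepted by the central overread.
- If the first sample was rejected and the retest accepted, the retest is baseline.
- If neither was accepted, baseline sputum is missing.

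Leave the window rule for Visits 3 to 7 as it is. The visible protocol describes the overread only for Visit 2 and its retest, and poor samples at later visits are not repeated, so a wider restriction could remove follow-up values without a stated basis. Reconcile the text with Protocol 7.3.1.3 by stating whether the retest counts as part of Visit 2. If a section not shown already excludes rejected samples, a cross-reference from 6.7 is enough.

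The cost is a short addition to SAP 6.7 and an acceptance flag in the baseline selection step. No new subject data are needed. The overread decision was already made to steer sputum collection, but the documents do not show that it is in the analysis database, so it may have to be transferred.

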3.3.4 Patients with COPD and A1AT deficiency

3.3.4.1 Inclusion criteria

1. All patients must sign an informed consent consistent with ICH-GCP guidelines prior to participation in the study, which also includes the application of study restrictions.
2. Patients must have a documented (prior to Visit 2) A1AT deficiency of ZZ genotype (see [appendix 10.4.4](#)).
3. Patients must be male or female outpatient.
4. Patients must be ex-smokers for at least 9 months with a smoking history of ≥ 10 pack years (see [appendix 10.4](#), calculation of number of pack years).
5. Patients must have a current diagnosis of mild, moderate or severe COPD made by a physician prior to or during Visit 1 and an mMRC score of 1 or more. The diagnosis of COPD must be in accordance with the GOLD Guidelines [[P15-01740](#)] and must be documented by the following criteria:
Known relatively stable airway obstruction with a post-bronchodilator FEV₁ of $\geq 30\%$ of predicted normal and a post-bronchodilator FEV₁/FVC $< 70\%$.
6. Patients must be between the ages of ≥ 30 and ≤ 70 years.
7. Patients must have a body mass index (BMI) of ≥ 18 and ≤ 35 kg/m².
8. Patients must be able to perform all study related procedures including technically acceptable pulmonary function tests, body plethysmography, D_{LCO}, sputum induction (if applicable), and chest CT.
9. Patients must be on stable therapy (not limited to respiratory medication) for the last 4 weeks prior to Visit 1.

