5.9.2 Vital Signs

Vital signs (blood pressure, pulse rate) will be taken at Visit 1, 5, 6, and 7. Systolic and diastolic blood pressure (BP) and pulse rate (PR) will be measured after the subject has rested for at least 5 minutes in a supine position. All measurements of an individual subject shall be made using the same blood pressure recording instrument on the same arm. The method, the identifier of the blood pressure recording instrument and the arm must be recorded in the source documents.

The measured vital signs will be documented on the source documents and recorded in the eCRF.

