5.11 SYMPTOM QUESTIONNAIRES

5.11.1 mMRC

The Modified Medical Research Council Dyspnoea Scale (mMRC) [[R00-0206](#)] should be completed by COPD patients as the first questionnaire during a study visit, prior to the CAT and SGRQ, pulmonary function testing and all other procedures. The mMRC will be completed at Visit 1, 2, 5, 6, and 7.

The mMRC uses a simple grading system to assess a patient's level of dyspnoea. All questions relate to everyday activities and are generally easily understood by patients. Scores range from 0 (none) to 4 (very severe) and are usually obtained in a few seconds.

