4.2 CHANGES

There were no changes to the planned analyses as compared to what was described in the CSP. However, the structure of the planned analyses in the TSAP is not consistent to Section 7 of the CSP. This change was necessary to allow for a better understanding of order and importance of the conducted analyses.

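### SAP Table 6.7:8 takes the mMRC baseline from the screening visit, against the protocol's definition of baseline and the SAP's own selection rule, and does not declare the change

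*SAP*

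**What the plan says.** **Protocol.** Section 5.11.1 schedules the scale: "The mMRC will be completed at Visit 1, 2, 5, 6, and 7". The flowchart agrees, and its footnote 4 limits the questionnaire to patients with COPD or COPD with A1AT deficiency. On the scale itself: "Scores range from 0 (none) to 4 (very severe"). Section 7.3 names mMRC among the clinical variables to be analysed. Section 7.3.1.3 gives the definition: "Baseline values are defined as the last measurement taken by the end of Visit 2". For comparing baseline assessments across groups, the same section says "logistic regressions for ordinal and categorical variables will be conducted". Inclusion criterion 5 for A1ATD patients (3.3.4.1) asks for a COPD diagnosis "made by a physician prior to or during Visit 1 and an mMRC score of 1 or more"; criterion 5 in 3.3.3.1 applies the same score threshold to the other COPD patients.

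**SAP.** Table 6.7:8 covers mMRC, CAT and SGRQ. Its baseline row is Visit 2, planned day 1, with a footnote: "Visit 1 for mMRC (Screening"). Section 6.7 makes the initial Visit 2 study day 1 and, when a window holds several values, takes the one nearest the planned day. Section 4.2 states: "There were no changes to the planned analyses as compared to what was described in the CSP". Sections 4.1 and 4.3 do not mention mMRC either.

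**The concern.** The footnote singles out one questionnaire and gives it an earlier baseline than the protocol would. Nothing in the visible text explains why, and the SAP says that nothing has changed.

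The choice matters because of which value it picks. The mMRC was an entry criterion, so the screening score is probably the one on which patients were selected. If so, grade 0 cannot occur at baseline in an eligible patient but can occur at every later visit. Patients whose screening score happened to be high pass the threshold and tend to score lower when asked again. In a study of disease progression, a table of mMRC by visit would then lean towards apparent improvement after baseline for a reason unrelated to the disease.

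The outputs exposed are the baseline questionnaire tables (SAP, baseline characteristics), the summaries at each time point (Protocol 7.3.1.1) and any group comparison of baseline mMRC under Protocol 7.3.1.3.

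**Working it through.** The SAP gives no figure to reproduce for the mMRC, so the check sets the rules side by side.

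**1. Which visit does each rule select?**

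| Source | mMRC baseline |
|---|---|
| Protocol 7.3.1.3, last value by the end of Visit 2 | Visit 2 |
| SAP Table 6.7:8, row entry | Visit 2, planned day 1 |
| SAP 6.7, value nearest the planned day | Visit 2 (step 2) |
| SAP Table 6.7:8, footnote 1 | Visit 1 |

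**2. The nearest-day rule.** The baseline window is day 28 or earlier, so it holds both visits. Distance = |visit day − 1|. Visit 2 is on day 1: |1 − 1| = 0. Visit 1 is on day −28 to −1 in the flowchart: |−28 − 1| = 29 down to |−1 − 1| = 2. With screening at eight weeks (Protocol 6.1.1.4), day −56 gives 57. Visit 2 is nearer in every case.

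**3. Is there a precedent in the SAP?** Table 6.7:9 also has a Visit 1 baseline, for physical examination and vital signs. There it is unavoidable: "Vital signs (blood pressure, pulse rate) will be taken at Visit 1, 5, 6, and 7". Protocol 5.9.1 gives the same visits for the physical examination. Neither is done at Visit 2, whereas mMRC is, so that reason does not carry over.

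**4. Is the Visit 1 value the selected one?** Probably. Protocol 6.2.1 assesses eligibility at Visit 1. However, criterion 5 ties only the diagnosis to Visit 1 and names no visit for the score, so the truncation is an inference.

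**5. Direction under assumed inputs.** None of these inputs is in the documents: a latent normal score with SD 1 and mean 0.8 to 1.6, rounded to grades 0 to 4, test-retest reliability 0.6 to 0.9, entry on Visit 1 of at least 1, and no true change. Among those entered, mean mMRC goes from 1.867 at Visit 1 to 1.821 at Visit 2 (−0.05) at reliability 0.9 and mean 1.6. It goes from 1.466 to 1.196 (−0.27) at reliability 0.6 and mean 0.8. This shows the direction of the effect and is not an estimate for this study.

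**6. BODE.** The index is calculated at Visit 2 (Protocol 6.2.2), has a Visit 2 baseline (SAP Table 6.7:3) and contains mMRC (Protocol Appendix 10.6). A patient's reported baseline mMRC and the mMRC inside the baseline BODE can therefore come from different visits. Grades 0 and 1 both score 0 BODE points, so only a difference involving grade 2 or higher would show in the index.

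**7. FEV1 index (editorial).** SAP 7.4.1 runs k from 1 to 7 and calls k a visit. Table 6.7:1 has six spirometry windows, Visits 2 to 7. Visit 1 shares the baseline window with Visit 2 and loses by the arithmetic in step 2. The rules thus yield at most six records per subject, or five if the Visit 3 FEV1 is not used. Protocol 5.4 describes that Visit 3 value as a safety check for sputum induction, which may be made on a local device.

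**The case against.** Four objections deserve weight.

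- **No mMRC change analysis is visible.** Protocol 7.3.1.1 and SAP 5 define change from baseline for continuous variables, and the mMRC is a five-grade scale. The questionnaire definitions (SAP 5.3.4) are not in the text available. This stands. A reader might infer that a planned mMRC progression result is biased; the documents do not show that such a result exists. What remains are the baseline tables and by-visit description.
- **The truncation is inferred.** Some criteria are re-checked at Visit 2 (Protocol 6.2.2), and the documents do not say whether mMRC is among them. If it is, grade 0 is closed at Visit 2 as well, and moving the baseline would remove little of the selection effect. This stands as a limit on the consequence, but not on the conflict between the two documents.
- **A reason may exist.** In SAP 6.7 the heading for the baseline definition is followed directly by the windowing text, so some text may not have reached us. That is not counted as missing. Even with a reason, the footnote departs from Protocol 7.3.1.3 while SAP 4.2 declares no change.
- **mMRC is minor here.** It is not among the main outcomes in SAP 5.1 and is not collected in the controls. This is correct and limits the weight of the point.

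A reader might also infer from k = 1 to 7 that the screening FEV1, which assigns the control or GOLD group, enters the slope and biases the group comparison. The documents do not support this. The windows, the nearest-day rule and the Visit 2 timing anchor in SAP 6.6.3 all exclude Visit 1 when Visit 2 exists. The lung-density model in the same section uses protocol visit numbers (5, 6, 7), so the index is most likely a slip in visit numbering. Any size for such a bias would rest on assumed populations.

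**Conclusion.** The mMRC footnote is wrong as written. It conflicts with the protocol's definition of baseline, with the visit in its own table row and with the SAP's selection rule, and the departure is not declared. This follows from the text and needs no assumption.

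The consequence is more tentative. If the entry score was taken at Visit 1, the reported baseline is truncated at grade 0 and by-visit descriptions are open to regression to the mean. No size of bias can be given, because the share of patients who would read grade 0 at Visit 2 is not in the documents. No main outcome is affected. The FEV1 index is an editorial inconsistency with no claimed effect on the slope.

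**What to change.** In SAP Table 6.7:8, replace footnote 1 by: *mMRC: last value by the end of Visit 2 (Visit 1 only if Visit 2 is missing).* If there is a reason to keep Visit 1, state it in SAP 4.2 as a departure from Protocol 7.3.1.3. The cost is SAP wording and re-derivation of the mMRC baseline; no new data are needed, and there is no other downside.

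Editorial, in SAP 7.4.1: let k index the spirometry records selected by Table 6.7:1, state whether the Visit 3 safety FEV1 enters the model, and confirm that the SAS code cited as Section 9.5.2 does the same.
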